#### 5. Primary Endpoint

##### Primary Endpoint

#1: The proportional change from baseline in the area under the curve (AUC) for NT Pro BNP levels measured at baseline, weeks 2, 4, 8, 12 and 24.

See Section 9 for a detailed description of the primary endpoint, including rules used for handling incomplete data.

#### 6. Secondary Endpoints

##### Secondary Endpoints (Efficacy)

#1: Days alive and out of hospital at 24 weeks, not listed for transplant (Status 1A, 1B or 1-4) or undergoing transplant, implanted with an LVAD, maintained or started on continuous inotropic therapy for  $\geq 7$  days, or has had two hospital admissions for heart failure (HF), other than the index admission. The days alive and out of hospital will end on the day of the second HF readmission, if applicable.

##### Secondary Endpoints (Tolerability)

#2: Tolerability measured as number of subjects achieving a target dose of 25%, 50% or 100% of valsartan or LCZ696.

#3: Tolerability measured as number of subjects developing hypotension (SBP  $\leq 85$  mmHg) with symptoms.

#4: Tolerability measured as number of subjects developing worsening renal function (eGFR  $< 20$  ml/min/1.73m^2).

#5: Tolerability measured as number of subjects developing moderate ( $> 5.5$  mmol/L) or severe ( $\geq 6$  mmol/L) hyperkalemia.

See Section 10 for a detailed description of each secondary endpoint, including rules used for handling incomplete data.

#### 7. Tertiary Endpoints

##### Tertiary Endpoints

#1: Time to death through 24 weeks.

- #2:** Time to cardiovascular death through 24 weeks.
- #3:** Time to first heart failure hospitalization through 24 weeks.
- #4:** Time to death or first heart failure hospitalization through 24 weeks.
- #5:** Time to cardiovascular death or first heart failure hospitalization through 24 weeks.
- #6:** Total number of HF hospitalization admissions through 24 weeks.
- #7:** Number of subjects on continuous inotropic therapy  $\geq 7$  days after discharge from the index hospitalization through 24 weeks.
- #8:** Number of subjects listed for transplant (1A, 1B or 1-4), transplanted or implanted with an LVAD through 24 weeks.
- #9:** Change in eGFR levels compared to baseline. Renal function was assessed at baseline, weeks 2, 4, 8, 12, and 24.
- #10:** Change in cystatin C levels compared to baseline. Renal function was assessed at baseline, weeks 2, 4, 8, 12, and 24.
- #11:** Number of subjects with unanticipated use of IV diuretics (outpatient, ER or inpatient) through 24 weeks.
- #12:** Change in AUC in the Kansas City Cardiomyopathy Questionnaire (KCCQ) at 4, 12, and 24 weeks compared to baseline.
- #13:** The change in the AUC for the ratio of NT Pro BNP/BNP from baseline to weeks 2, 4, 8, 12, and 24.
- [Note: Tertiary Endpoint #13 will only be assessed on the first 200 patients randomized, as generated for the Interim Analysis. A decision was made by the Executive Committee to not assay for BNP at trial completion for the remaining randomized patients]

See Section 11 for a detailed description of each tertiary endpoint, including rules used for handling incomplete data.

## 8. Exploratory Endpoints

### Exploratory Endpoint

**#1:** A four level modified clinical composite endpoint including 1) death, 2) LVAD or Heart Transplant (including listing status of 1A, 1B or 1-4), 3) multiple HF hospital admissions, and 4) single HF admission.

See Section 12 for a detailed description of each tertiary endpoint, including rules used for handling incomplete data.

[figure not shown]
## 9. Endpoint Descriptions

### 9.1 – Primary Endpoint

**Endpoint Description:** The log of the proportional change from baseline in the area under the curve for the ratio of NT Pro BNP compared to baseline, using the pre-COVID-19 population.

**Response Variable Definition:** All available time points will be used in the calculations. NT Pro BNP is measured at Baseline, Week 2, Week 4, Week 8, Week 12 and Week 24. The ratio of each of the post-Baseline measures will be calculated versus Baseline. The area under the entire piecewise dataset is the response variable. A visual example is provided showing a patients' hypothetical data for NT Pro BNP ratio to Baseline.

This area is determined by calculating the sum of the areas of each of the individual trapezoids. Each trapezoidal area is composed of the area bordered by the time interval on the x-axis (e.g., 0 to 2 Weeks), the respective NT Pro BNP ratio at each of the time points on the y-axis (e.g., 1 at x=0 and 0.7 at x=2), and the line segment connecting the NT Pro BNP ratios between the two y-axis values (1 and 0.7). The number of trapezoids available will depend on the completeness of the data.

It is expected that NT Pro BNP measurements may not be measured exactly at the specified time points. For example, the measurement corresponding to the 12 Week time point may actually be measured for example at 11 or 12.5 Weeks after randomization. In calculating the AUC, the measurement corresponding to Baseline will always be set at the 0 time point. Each post-Baseline visit will use the value for the visit timing, even if that timing is not exact (e.g., Week 12 visit will always assign a 12 for the x-axis). The final step in the calculation is to take log of the calculated area under the curve.

Additional Covariates in Addition to Randomized Treatment: Baseline log NT Pro BNP, atrial fibrillation status, random effect of patient

Handling of Dropouts and Missing Data: If missing NT Pro BNP at Week 24, use last observation carried forward (LOCF) from previous post-Baseline time point with available NT Pro BNP data. No adjustment will be made for missing Baseline results.

Sensitivity Analysis: Several sensitivity analyses will be performed.

- 1) Complete cases, using patients with available Baseline and Week 24 Week 24 NT Pro BNP data
- 2) For patients missing Week 24 value, impute 2.5xBaseline value for Week 24

[Note: The sensitivity analysis using imputation of 2.5xBaseline value will not be performed due to the concern that the impact of missing data due to the COVID-19 pandemic might overstate the effect of the imputation.]

- 3) For patients missing Week 24 value, impute 5xBaseline value for Week 24

[Note: This sensitivity analysis using imputation of 5xBaseline value will not be performed due to the concern that the impact of missing data due to the COVID-19 pandemic might overstate the effect of the imputation.]

- 4) For patients that receive a left ventricular assist device (LVAD) or heart transplant prior to the Week 24 assessment, remove all NT Pro BNP results post-procedure due to the potential for an artificial response due to the procedural impacts on the heart. Missing values will be imputed in the same fashion as in the primary analysis.
- 5) To address a potential question seen in some journal reviews, the primary model will be run again, adding a new covariate for the effect of enrolling site.
- 6) Wilcoxon with worst rank imputation based on time to death and then ranking worst to best NT Pro BNP AUC for those patients that did not die prior to 24 week visit
- 7) Re-calculate the primary endpoint analysis and the remaining sensitivity analyses using the original ITT population.

Statistical Tests: For the Primary and Sensitivity Analyses 1 – 5, a mixed model (PROC MIXED in SAS) will be used to test the significance of differences in the area under the curve for the Log(NT Pro BNP AUC) between the two treatment arms.

For Sensitivity Analysis 6, a Wilcoxon test (PROC NPAR1WAY in SAS) will be used to test whether there is a difference in the distribution of ranks between the two treatment arms.

Interpretation of Results: A lower value for the AUC indicates an improvement in the LCX696 arm versus the Valsartan arm. Lower rank scores indicate worse outcomes in the worst rank analysis.

---

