16.2 Sample Size Justification and Randomization

Subjects will be randomized in a 1:1 allocation ratio using a permuted block design with stratification based on the clinical center and atrial fibrillation status. We plan to randomize 400 subjects with planned follow-up of 26 weeks. The primary efficacy endpoint is the proportional change from baseline in the AUC for NT-proBNP levels measured at 2, 4, 8, 12 and 24 weeks.

Based on recent Heart Failure Clinical Research Network (HFN) trials with similar follow-up requirements, we are anticipating a dropout / withdrawal of consent rate of approximately 5%. However, due to deaths and other sample collection issues we anticipate as many as 20-25% of subjects will not have NT-proBNP data at the week 24 assessment.

For the primary analysis, the AUC data will be log transformed and subjects missing the NT-proBNP data at the week 24 assessment will be assigned the last observation carried forward (LOCF). Based on a 2-sample t-test with type I error of 0.05 two-sided, the total sample size of 400 randomized subjects will provide 80% and 90% power to detect a differences of 19% and 21% for LCZ696 compared to valsartan. The PARAMOUNT phase II clinical trial observed a 23% greater reduction in NT-proBNP for LCZ696 compared to valsartan at 12 weeks post-randomization in patient population with HFpEF. ⁶ The HF Network investigators believe a 20% reduction in NT-proBNP would be considered a clinically significant improvement, and this level of change falls within a range considered clinically meaningful in a recent comparative effectiveness review published by AHRQ. ⁷

Sensitivity analyses will examine the influence of the imputation for the informatively missing data. For the complete case analysis, the total sample size of 400 subjects will provide approximately 80% and 95% power to detect reductions of 20% and 25% for LCZ696 compared to valsartan, respectively. These calculations were based on a two-sample t-test and assume that the standard deviation of the log-transformed 180-day AUC measure is 0.70. ⁸

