16.4 Analysis of the Primary Endpoint

A general linear model will be used to estimate and statistically compare the log-transformed AUCs in the NT-proBNP values between the two treatment groups. Each individual will have one response based on the log of the proportional change from baseline in the AUC from the 2, 4, 8, 12, and 24 week measurements. Missing data for the NT-proBNP assessment at week 24 will be assigned the last observation carried forward (LOCF). The treatment effect will be summarized using a point estimate and 95% confidence interval.

Sensitivity analyses will examine the influence of the imputation for the informatively missing data and the possibility for outliers due to clinical changes including atrial fibrillation status. For a set of analyses, missing data for the NT-proBNP assessment at week 24 will be assigned a value corresponding to 2.5 and 5 times the baseline NT-proBNP value. The linear models will include covariates for the treatment group indicator variable, log of the baseline NT-proBNP, and atrial fibrillation status. A complete case analysis will be conducted to examine the sensitivity of the overall findings to the imputation algorithm. A nonparametric sensitivity analysis will compare the AUC data for NT-proBNP using a Wilcoxon test with a worst-rank imputation based on the time-to-death.⁹

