#### \* Analysis Modifications to Address COVID-19 Pandemic

The coronavirus COVID-19 pandemic has had a major impact on the performance of the LIFE trial. It was anticipated that patients will have greater difficulty attending study visits on their planned schedule due to restrictions on outpatient visits at many institutions. Therefore, patients will be unable to participate in study-related procedures such as biomarker sample collection, which comprises the primary endpoint for this trial. Additionally, due to restrictions on clinic access and potential concerns with patients going to the emergency department where exposure risk to COVID-19 is increased, we expect reporting of clinical endpoints such as emergency department visits and even hospital admissions to be impacted by the pandemic.

Therefore, due to the unexpected disruption brought on by the COVID-19 pandemic, the analysis plan was amended to restrict the reported program analyses to those patients that had their Week 12 visit prior to March 1, 2020, when the COVID-19 pandemic became more active in the continental United States. This translated to restricting the reported analyses to patients that were randomized on December 7, 2019 or earlier. Additionally, any study data collected after March 1, 2020 were excluded from the analyses for those patients randomized on or prior to December 7, 2019. This amended population will be labeled as the pre-COVID-19 population within the analysis plan.

The original protocol-specified analyses were to be conducted on all randomized patients using all available information. Those analyses will still be performed but will be considered to be sensitivity analyses.

Of the 365 patients randomized, 335 will be included in the pre-COVID-19 population. Twenty five of the 335 patients will have some visit information removed due to study visits occurring March 1, 2020 or later. The

remaining 30 patients will only contribute to the original protocol-specified analyses, now part of the sensitivity analyses.

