## 11.12 – Tertiary Endpoint #12

Endpoint Description: Change in AUC in the Kansas City Cardiomyopathy Questionnaire (KCCQ) compared to baseline – both for overall and clinical summary scores, using the pre-COVID-19 population.

Response Variable Definition: The KCCQ questionnaire was completed at Screening (considered Baseline for this analysis), Week 4, Week 12 and Week 24. The endpoint will be derived in a similar fashion to the primary endpoint (see 9.1).

Additional Covariates in Addition to Randomized Treatment: atrial fibrillation status at time of randomization, appropriate baseline value of each KCCQ score

Handling of Dropouts and Missing Data: If missing KCCQ score at Week 24, use last observation carried forward (LOCF) from previous post-Baseline time point with available KCCQ score data. No adjustment will be made for missing Baseline results.

Sensitivity Analysis: Re-calculate the endpoint analysis using the original ITT population.

Statistical Tests: A general linear model (PROC GLM in SAS) will be used to test the significance of differences in the area under the curve for the each KCCQ score between the two treatment arms.

Interpretation of Results: A higher KCCQ score indicates an improved KCCQ score in the LCZ696 arm versus Valsartan.

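### SAP 11.9 and 11.10 leave the collected baseline out of the renal change models, and SAP 9.1 gives a random patient effect to a response with only one value per patient

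*SAP*

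**What the plan says.** **Primary model.** Protocol 16.4 states "A general linear model will be used to estimate and statistically compare the log-transformed AUCs in the NT-proBNP values" and, on the data structure, "Each individual will have one response based on the log of the proportional change from baseline in the AUC". Its next paragraph, on sensitivity analyses, adds "The linear models will include covariates for the treatment group indicator variable, log of the baseline NT-proBNP, and atrial fibrillation status". SAP 9.1 also forms one area per patient from the trapezoids and then takes its log. The terms besides treatment are "Baseline log NT Pro BNP, atrial fibrillation status, random effect of patient". For the primary analysis and Sensitivity 1 to 5, "a mixed model (PROC MIXED in SAS) will be used to test the significance of differences in the area under the curve". Sensitivity 2 and 3 have since been withdrawn, and Sensitivity 7 reruns the remaining analyses in the ITT population. No covariance structure or degrees-of-freedom method is given.

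**Comparable AUC endpoints.** SAP 11.12 (KCCQ) and 11.13 (NT-proBNP/BNP) refer back to 9.1 for their derivation. For KCCQ, "A general linear model (PROC GLM in SAS) will be used to test the significance of differences in the area under the curve". SAP 11.13 also uses PROC GLM. Neither has a patient effect, and both adjust for baseline.

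**Renal change models.** SAP 11.9 and 11.10 fit a mixed model to the change in eGFR and in cystatin C over several visits. AF status is the only covariate besides treatment. Protocol 16.5 assigns longitudinal data to mixed models and names no renal covariates.

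**Visits.** SAP Section 7 (#9, #10), 11.9 and 11.10 include Week 2. Protocol 13.3 item 7 lists baseline and Weeks 4, 8, 12 and 24.

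**The concern.** A random patient effect needs at least some patients with repeated responses. Here there is one row per patient, so the model contains a variance component that the data cannot estimate. The primary p-value then depends on how the software assigns denominator degrees of freedom, which neither document fixes. The term is also an unexplained departure from protocol 16.4.

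In the renal models, the baseline value enters the change score but is not a covariate. The SAP adjusts for baseline in 9.1, 11.12 and 11.13, so 11.9 and 11.10 are out of line with its own practice and give up precision that needs no new data.

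The Week 2 cystatin C visit raises a simpler question: whether the data that the SAP says it will model exist.

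**Working it through.** **1. The planning SD.** Protocol 16.2 assumes SD 0.70 for the log AUC and gives complete-case power of about 80% and 95% for reductions of 20% and 25%. With 22.5% missing (midpoint of the stated 20–25%), each arm has 200 × 0.775 = 155. SE = 0.70 × √(2/155) = 0.0795.
- 20%: −ln(0.80) / 0.0795 = 0.2231 / 0.0795 = 2.81, power 80.1%.
- 25%: 0.2877 / 0.0795 = 3.62, power 95.1%.

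The figures reproduce, so SD 0.70 is used in step 4.

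**2. Identifiability.** Write y = Xb + Zu + e, where X holds intercept, treatment, log baseline NT-proBNP and AF status. With one row per patient Z = I, so Var(y) = (σ²ᵤ + σ²ₑ)I. The likelihood depends only on the sum. Two independent simulated datasets with N = 335 were fitted with the patient share of a fixed total variance set to 0, 25, 50, 75 and 100%:

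| Dataset | Treatment estimate | SE | REML log-likelihood |
|---|---|---|---|
| A | −0.13597 | 0.07749 | −51.5116 |
| B | −0.06549 | 0.07936 | −69.2917 |

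Each row was identical at all five splits. In dataset B the estimate and SE were also checked against ordinary least squares and matched.

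**3. Degrees of freedom.** Rank X = 4 and rank[X Z] = N.

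| Analysis | N | N − rank X | N − rank[X Z] |
|---|---|---|---|
| Primary, pre-COVID-19 population | 335 | 331 | 0 |
| ITT rerun | 365 | 361 | 0 |
| Complete cases, 20–25% missing | 268 to 251 | 264 to 247 | 0 |
| Complete cases, also losing 25 patients | 248 to 232 | 244 to 228 | 0 |

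The values for 335 and 365 are upper limits, because patients without a baseline or any post-baseline value drop out. The third row applies the protocol's planning figure ("we anticipate as many as 20-25% of subjects will not have NT-proBNP data at the week 24 assessment") to 335. The fourth applies it to 335 − 25 = 310, on the assumption that every patient affected by the cut-off loses Week 24 ("Twenty five of the 335 patients will have some visit information removed due to study visits occurring March 1, 2020 or later"). Sensitivity 5 has fewer because of its site term.

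**4. Effect on the test.** Take a 20% reduction at N = 335. SE = 0.70 × 2/√335 = 0.0765 and t = ln(0.80)/0.0765 = −2.917. Then p = 0.0038 at 331 df and 0.0035 with a normal reference. Under N − rank[X Z] there is no p-value.

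**5. Renal baseline, single visit.** With equal variance σ² at baseline and follow-up and correlation r, the change score has variance 2σ²(1 − r) and the baseline-adjusted outcome has σ²(1 − r²). The ratio is (1 + r)/2. The documents give no r, so a range is assumed.

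| r | Variance reduction | SE multiplied by | 335 unadjusted equals adjusted | Power, if 80% unadjusted |
|---|---|---|---|---|
| 0.5 | 25% | 0.866 | 335 × 0.75 = 251 | 89.9% |
| 0.7 | 15% | 0.922 | 335 × 0.85 = 285 | 86.0% |
| 0.9 | 5% | 0.975 | 335 × 0.95 = 318 | 82.0% |

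A simulation of 4,000 trials per correlation, with AF in both models, gave variance reductions of 24.8%, 15.0% and 6.0%. Both estimators were centred on zero when there was no effect.

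**6. Week 2, side by side.** Protocol 12.2 lists only BNP and NT-proBNP for core testing at Visit 3, and Appendix A footnote 3 agrees. Protocol 18.3 nevertheless schedules a Week 2 plasma specimen. Routine testing at Visit 3 includes creatinine, so Week 2 eGFR can be computed. The doubt over data is confined to cystatin C.

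**The case against.** **The random effect is harmless.** Largely right. A reader might infer that the primary result is biased or its p-value untrustworthy, and the documents do not support that. The estimate and SE are those of the linear model, and the rules in step 4 that return a p-value agree closely. The one failing rule is an assumption and would fail visibly when run. What stands is that a prespecified primary model should not contain a parameter that cannot be estimated.

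**A repeated-measures model was meant.** Both documents reduce each patient to one response. Had it been meant, the visit-level response and covariance would still need defining.

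**Protocol 16.4 does not give these covariates for the primary model.** A reader might infer that it does. Its primary paragraph names a general linear model and one response but no covariates; the covariate sentence follows the 2.5-fold and 5-fold imputations. Applying it to the primary analysis is an interpretation. The recommended terms are in any case the SAP's own fixed effects.

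**Renal adjustment is optional.** Unadjusted change is valid under randomization, and the protocol does not require a baseline covariate, so neither bias nor a protocol conflict can be claimed. The percentages describe one visit, whereas 11.9 and 11.10 plan a multi-visit model whose gain will differ. SAP Section 14 also reports the interim efficacy analysis as done, so this is a late change and should be documented as such.

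**Week 2 is only half a discrepancy.** Agreed. Protocol 13.3 omits Week 2 for both markers, but creatinine is scheduled then, so it does not follow that Week 2 eGFR lacks data.

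**Conclusion.** The point holds in three limited parts.

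- **Renal models.** Leaving baseline out of 11.9 and 11.10 costs precision on two tertiary endpoints: 5% to 25% of the variance at a single visit for correlations from 0.9 down to 0.5, assuming equal variances. The correlations are assumed. There is no bias.
- **Primary model.** The random patient effect in 9.1 is not estimable and departs from protocol 16.4 and from SAP 11.12 and 11.13. The estimate and SE are unaffected. The residual df should be at most 331 in the primary analysis. Inference is lost only under an N − rank[X Z] rule, which is an assumption here.
- **Week 2 cystatin C.** The SAP and the protocol's assay lists disagree. This is minor.

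All three deserve correction in the SAP. None puts the primary treatment estimate at risk.

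**What to change.** 1. **SAP 11.9 and 11.10:** add baseline eGFR and baseline cystatin C, respectively, as covariates.
2. **SAP 9.1:** delete the random patient effect. Fit treatment, log baseline NT-proBNP and AF status for the primary analysis, Sensitivity 1, 4 and 5, and their ITT reruns under 7. Sensitivity 5 keeps its site covariate. PROC GLM, or PROC MIXED without a patient effect, gives the same fit.
3. **Week 2 cystatin C:** reconcile SAP Section 7 (#10) and 11.10 with protocol 12.2, 13.3, 18.3 and Appendix A, by removing the visit or documenting that the stored specimen was assayed. Week 2 eGFR can stay.

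The cost is SAP wording and minor programming, with no new data. Item 2 leaves the primary estimate and SE as they are. Item 1 changes the tertiary renal models, so it should be dated and approved before treatment codes are opened, as protocol 16.1 requires for planned analyses. If that is no longer possible, the adjusted renal results should be labelled supplementary.

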9 PATIENT POPULATION

9.1 Study Population

It is anticipated that approximately 400 subjects meeting eligibility criteria listed below will be randomized into the study. Subjects suitable for this protocol are individuals with advanced HF and a LVEF \leq 35%. Subjects may be currently hospitalized or non-hospitalized.

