9.2 Inclusion Criteria

Key inclusion criteria

1. Advanced HF \geq EF defined as including ALL
 - a. LVEF \leq 35% documented during the preceding 12 months
 - b. NYHA class IV symptomatology, defined as chronic dyspnea or fatigue at rest or on minimal exertion in the previous 3 months, or patients who require chronic inotropic therapy
 - c. Minimum of 3 months GDMT for HF and/or intolerant to therapy
2. Systolic blood pressure \geq 90 mmHg
3. Serum NT-proBNP \geq 800 pg/mL OR BNP \geq 250 pg/mL (most recent - less than 3 months old)
4. Any one or more of the following objective findings of advanced HF including:

- a. Current inotropic therapy or use of inotropes in the past 6 months
 - b. ≥ 1 hospitalization for heart failure in the past 6 months (not including the index hospitalization for inpatient participants)
 - c. LVEF $\leq 25\%$ (within the past 12 months)
 - d. Peak VO₂ $< 55\%$ predicted or peak VO₂ ≤ 16 for men or ≤ 14 for women (Respiratory Exchange Ratio (RER) ≥ 1.05) (within the past 12 months)
 - e. 6 min walk test distance < 300 m (within the past 3 months)
5. Age ≥ 18 years and ≤ 85 years
 6. Signed Informed Consent form

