10.8 Randomization, Stratification and Blinding

Subjects will be consented and enrolled at the first study visit. This will be followed by a run-in phase. Subjects who successfully tolerate the study drug during the run-in phase will be randomized at the second study visit. Subjects will be randomized using procedures determined by the CC to one of 2 treatment groups. Subjects will be randomized in a 1:1 allocation ratio using a permuted block design with stratification based on the clinical center and atrial fibrillation status. Subjects will be randomized using a permuted block randomization to ensure relatively equal distribution of subjects to each arm within each site.

Blinding of the study, with respect to treatment groups, will be preserved by the use of matching placebo, identical in appearance to the active study drugs. The investigator may be asked at the end of the trial if they had obtained any information which may have led to the unbinding of treatment.

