### 2.2 Randomization

Patients are randomized in a 1:1 ratio to either LCZ696 + Valsartan-placebo or Valsartan + LCZ696-placebo. The randomization scheme consists of a permuted block design with stratification by clinical site and atrial fibrillation status.

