## 10. Secondary Endpoint Descriptions

### 10.1 – Secondary Endpoint #1

Endpoint Description: Days alive and out of hospital at 24 weeks, not listed for transplant (Status 1A, 1B or 1-4) or undergoing transplant, implanted with an LVAD, maintained or started on continuous inotropic therapy for  $\geq 7$  days, or has had two hospital admissions for heart failure (HF), other than the index admission. The days alive and out of hospital will end on the day of the second HF readmission, if applicable, using the pre-COVID-19 population.

Response Variable Definition: Each component of the endpoint will have daily flags created indicating whether the patient met the endpoint on that specific day. Days will start at day of randomization (Day 0) and continue until a maximum of 163 (beginning of 24 week visit window). Determination of the final evaluable date will depend upon which component is under evaluation. Any data collected after 163 days post randomization will not count for this endpoint.

Days alive: If a patient died between randomization and 163 days post randomization, each day will be coded as a 0 if they were alive and will be coded as a 1 if the patient has previously died. All 163 post-randomization days will be evaluable if the patient died. If the patient had not died, the last evaluable date will be minimum of 163 days post randomization, date of Week 24 visit, date of withdrawn consent or date of loss to follow-up.

Out of hospital: If a patient was randomized while admitted to the hospital, each day the patient was in the hospital from randomization to discharge will be coded as a 1, otherwise the coded value will be a 0. For every other unplanned hospital admission, the patient will be coded as a 0 if they were not hospitalized and coded as a 1 if they were, using the admission and discharge dates as the anchors. The last evaluable date will be minimum of 163 days post randomization, date of Week 24 visit, date of withdrawn consent, date of death or date of loss to follow-up.

Not listed for transplant or undergoing transplant: If a patient either has been listed for heart transplant or received a transplant, each day will be coded as a 0 if they were not listed/transplanted and will be coded as a 1 if the patient had been listed or transplanted. The last evaluable date will be minimum of 163 days post randomization, date of Week 24 visit, date of withdrawn consent, date of death or date of loss to follow-up.

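### Hospital status at randomisation is in neither the strata nor the primary NT-proBNP model, at a modest cost in precision and in protection against chance imbalance

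*SAP*

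**What the plan says.** - **Who is enrolled.** Protocol 9.1: "Subjects may be currently hospitalized or non-hospitalized". No share, cap or quota is set. Protocol 9.2 counts earlier heart failure admissions "not including the index hospitalization for inpatient participants", so inpatients are expected to have an index stay.
- **Randomisation during an admission.** SAP 10.1 has a coding rule that begins "If a patient was randomized while admitted to the hospital". The status at randomisation can therefore be derived from data already collected.
- **Stratification.** Protocol 10.8 specifies "stratification based on the clinical center and atrial fibrillation status". SAP 2.2 agrees: "stratification by clinical site and atrial fibrillation status".
- **Primary model.** SAP 9.1 lists, besides treatment, "Baseline log NT Pro BNP, atrial fibrillation status, random effect of patient". Protocol 16.4 is consistent on the fixed terms: "The linear models will include covariates for the treatment group indicator variable, log of the baseline NT-proBNP, and atrial fibrillation status".
- **Elsewhere.** Hospital status is not among the seven sensitivity analyses in SAP 9.1 (the fifth adds enrolling site) or the subgroups in SAP 15.

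**The concern.** The response is the log of the 24-week AUC of NT-proBNP relative to the Visit 2 value. The protocol's hypothesis treats NT-proBNP as a marker of haemodynamics and clinical condition. An inpatient and an outpatient with the same Visit 2 value may follow different courses afterwards in either arm, because one baseline level cannot tell a long-standing plateau from a temporary peak. If so, setting is a prognostic factor that the model leaves in the residual.

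Two things are at stake. The residual variance is larger than it needs to be, so power is lower. And if one arm happens to receive more inpatients, the estimate in this one trial moves by an amount that a covariate would have removed.

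**Working it through.** **Inputs from the documents.** SD of log AUC 0.70, two-sided alpha 0.05, and a 20% reduction as the effect judged clinically meaningful (protocol 16.2); 1:1 allocation; 335 patients in the pre-COVID-19 population (SAP 3), about 167.5 per arm. A 20% reduction is −ln(0.80) = 0.223 log units.

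**Inputs not in the documents (assumed).** Inpatient share p = 15–40%. Inpatient versus outpatient difference in mean log AUC ratio, at equal baseline level, d = 0.2–0.6.

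**Step 1: reproduce the plan's figure.** Protocol 16.2 gives complete-case power of about 80% for a 20% reduction and 95% for 25%. With 20–25% of 400 missing at week 24, 150–160 per arm remain. Power = Φ(δ / [0.70·√(2/n)] − 1.96) gives 78.8–81.4% and 94.5–95.7%. Both reproduce, so 0.70 is a usable base.

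**Step 2: does the ratio scale add noise?** Every post-baseline value is divided by the same baseline, so log(AUC of ratio) = log(AUC) − log(baseline). With log baseline already a covariate, the treatment estimate is the same for the ratio and for raw log AUC; a numerical check gave −0.2394 both ways. The ratio adds no noise of its own. Only variation not predicted by baseline is at issue, which is how d is defined.

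**Step 3: variance explained.** R² = p(1−p)d² / 0.49.
- p = 0.15, d = 0.2: 0.0051/0.49 = 1.0%
- p = 0.30, d = 0.4: 0.0336/0.49 = 6.9%
- p = 0.40, d = 0.6: 0.0864/0.49 = 17.6%

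At the middle case the equivalent sample gain is 335/(1 − 0.069) − 335 ≈ 25 patients.

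**Step 4: power for a 20% reduction at n = 335.** Unadjusted: SE = 0.70·√(2/167.5) = 0.0765, power 83.1%. Adjusted SD = √(0.49 − p(1−p)d²):
- low corner: SD 0.696, power 83.5%
- middle: SD 0.676, SE 0.0738, power about 85.5%
- high corner: SD 0.635, SE 0.0694, power 89.5%

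The gain is about 0.4, 2.5 and 6.4 points.

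**Step 5: chance imbalance at the middle case.** SD of the between-arm difference in inpatient share = √(4·0.30·0.70/335) = 0.050, or 5 percentage points. Times 0.4, this moves the estimate by 0.020 log units: 9% of 0.223, and about a quarter of the standard error (0.020/0.0765 = 0.26).

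**Step 6: validity.** In simulations of 334 patients (3,000 runs per scenario; inpatient share 20–50%, extra inpatient fall 30–50%), type I error was 5.0–5.5% without the covariate and 4.7–5.1% with it. For a true effect of −0.223, mean estimates lay between −0.222 and −0.224 with either model.

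**Step 7: if 0.70 excludes this heterogeneity.** At the middle case the total SD becomes √(0.49 + 0.0336) = 0.724. Unadjusted power is then 80.6%, and adjustment restores 83.1%. The gain is again about 2.5 points.

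**The case against.** The strongest reply is that nothing is wrong with the plan. Baseline NT-proBNP is adjusted for, one stratification factor is in the model and the other is in a sensitivity analysis. That is conventional. Chance imbalance is already reflected in the standard error, and any omitted prognostic factor could be criticised in the same way. Both quantities that set the size of the gain are assumed. Blocking within site may already balance setting in part, if sites differ in where they recruit.

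Most of this stands, and it limits the point to efficiency. What remains is that setting is a specific, already identifiable baseline factor with a plausible link to the course of this marker, and that adjusting for it costs almost nothing.

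A reader might go further and infer that inpatients enter at a decompensated peak, that outpatients are stable, and that recovery falls distort the result. The documents do not support that. They give neither the reason for the index admission nor any NT-proBNP course after discharge. The baseline sample is taken at Visit 2, after 3–7 days of run-in (protocol 7.1 and 18.3), so it need not be an admission-day value. Outpatients must also have class IV symptoms and an objective marker of advanced disease (protocol 9.2).

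Timing is a fair objection to changing the primary model. SAP 14 reports an efficacy interim on the primary endpoint after 200 patients, with conditional power calculated. A covariate added afterwards invites the question of whether it was chosen with results in view.

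**Conclusion.** The point holds as an improvement in efficiency, of low to moderate severity. Hospital status is missing from the strata, the primary model, the sensitivity analyses and the subgroups, although both settings are enrolled. Readings to avoid are that the treatment estimate is biased, that the false-positive rate is inflated, or that dividing by baseline creates noise; steps 2 and 6 show none of these.

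On the assumed ranges (15–40% inpatients, residual difference 0.2–0.6), status explains about 1–18% of the variance and is worth roughly 0.4 to 6 points of power. At 30% and 0.4 the gain is about 2.5 points, from about 83% to about 85.5%. If the inpatient share or the residual difference is small, the gain is negligible.

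**What to change.** In SAP 9.1, add hospitalised versus not hospitalised at randomisation as a fixed covariate in the primary model. It then carries through to Sensitivity Analyses 1, 4 and 5 and to the original-ITT repeat in 7. Analyses 2 and 3 are not being performed, and 6 is a rank test without covariates. Record that the decision was made before final unblinding and without reference to interim results by arm.

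If that cannot be documented, leave the primary model as it is, prespecify the adjusted model as one further sensitivity analysis, and report hospital status by arm in the baseline table.

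The cost is one degree of freedom, a short SAP change and no new data, since the SAP 10.1 coding already needs the status. The downside is a departure from the covariates named in protocol 16.4, which should be stated and justified in the SAP.
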